9.2.2 Adverse drug reactions (ADRs)

All adverse events judged by either the investigator/delegate or the Sponsor as having a reasonable suspected causal relationship to an IMP qualify as adverse drug reactions (ADR). An unexpected ADR is an ADR of which the nature or severity, outcome or frequency is not consistent with the applicable reference safety information for the IP.

9.2.3 Serious adverse events (SAEs)

A serious adverse event is any untoward medical occurrence or effect that:

- results in death
- is life threatening (at the time of the event)
- requires hospitalisation or prolongation of existing inpatients' hospitalisation
- results in persistent or significant disability or incapacity
- is a congenital anomaly or birth defect
- is any other important medical event that did not result in any of the outcomes listed above due to medical or surgical intervention but could have been based upon appropriate judgement by the Site Investigator.

An elective hospital admission will not be considered as an SAE.

The Site Investigator or delegate will report all SAEs to the Sponsor without undue delay after obtaining knowledge of the events. Hospitalisations will be defined as at least one overnight stay. Hospitalisation for a pre-existing condition, including elective procedures planned prior to study entry, which has not worsened, does not constitute an SAE.

SAEs must be reported to the Sponsor by the person or nominated delegate who has discovered the SAE within 24 hours of becoming aware of the event. Some SAEs occurring within the 28-day follow-up period, may be identified retrospectively from diaries which will be received after 28 days. These will be reported within 24 hours of becoming aware of the event. The Sponsor or delegate will ensure SAEs being reviewed by the medical monitor for relatedness and expectedness as soon as possible, taking into account the reporting time for a potential suspected unexpected serious adverse reaction (SUSAR).

Procedure for immediate reporting of Serious Adverse Events

- The Study Site or national coordinating team will report all SAEs via the SAE form in the online data capture system 'Castor'. The study team at the Sponsor and the medical monitor will receive a notification about the SAE. GP, Study Site, national coordinating team will provide additional, missing or follow-up information in a timely fashion.
- If necessary, the participant may be contacted by GP practice to provide additional, missing or follow-up information as required.

A medical monitor will review the SAE once reported, collect information and report to the Sponsor within the SOP's timeframe. The Sponsor will submit an Annual Safety Report (ASR) including a list table of SAEs to all IECs and CAs of the participating countries (to all Member States concerned) through the CTIS once a year.

Expectedness

For SAEs that require reporting, expectedness of SAEs will be assessed and determined by the medical monitor, according to the relevant Reference Safety Information (RSI) section of the SmPC/IB. The RSI will be the current Sponsor and IEC/CTA approved version at the time of the event occurrence.

Assessment of Causality

The Site Investigator or delegate will report a first assessment of causality. For participants recruited centrally, an investigator, independent of the Sponsor, will make the first assessment of causality. The relationship of each SAE to the IP/control must be determined by a medically qualified individual according to the following definitions:

- Unrelated where an event is not considered to be related to the IP
- **Possibly** although a relationship to the IP cannot be completely ruled out, the nature of the event, the underlying disease, concomitant medication or temporal relationship make other explanations possible
- **Probably** the temporal relationship and absence of a more likely explanation suggest the event could be related to the IP
- **Definitely** the known effects of the IP, its therapeutic class or based on challenge testing suggest that the IP is the most likely cause

AEs/SAEs judged possibly, probably or definitely related will be considered as related to the IP.

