2.2 Secondary study objectives

The key secondary outcome will be early sustained recovery, which is defined recovery by day 14, sustained until day 28.

Other secondary objectives include assessment of the efficacy and safety of the study IP versus control on:

- Sustained recovery (participants' reported recovery that was maintained until 28 days)
- Time to first self-report of feeling recovered from individual symptoms of COVID-19 or COVID-like-illness (for Phase IIa type evaluation)
- Viral clearance (for Phase IIb and III type evaluation)
- Time to first self-report of return to usual daily activity
- Presence, duration and severity of individual respiratory symptoms
- Participant reported overall wellbeing
- Evaluation of overall safety of the IP by monitoring of (serious) adverse events and (serious) adverse drug reactions
- The use of additional antiviral medication
- The use of other prescribed and/or over-the-counter (OTC) medication for the RTI
- The occurrence of complications (hospitalisation, death; all-cause, non-elective hospitalisation will be assessed)
- Impact on usual daily activities
- Health care utilisation (e.g. general practitioner (GP) and hospital visits)
- Long-term (up to 6 months) consequences of COVID-19 or COVID-like-illness
- The incidence of COVID-19 and COVID-like-illness in other members of the household

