4.3 Exclusion criteria

The generic exclusion criteria are listed in this section. Potential additional exclusion criteria for individual IPs; for example, specific comorbidities or medication use, will be detailed in the ISA.

A potential participant who meets any of the following criteria will be excluded from participation in ECRAID-Prime:

- 1. Requiring admission to the hospital on the day of inclusion.
- 2. Known allergies or hypersensitivities to any of the components used in the formulation of the IP, or the control product.
- 3. Any disease, condition, or disorder, or language barrier that precludes participation in the trial, in the opinion of the GP or delegate (with GP serving as supervisor) checking eligibility and taking consent.
- 4. Any planned major surgery in the next 28 days.
- 5. Currently participating in a trial of a pharmacological treatment.

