8. METHODS

8.1 Study parameters/ endpoints

- 8.1.1 Primary study endpoints (phase dependent) will be:
- Time to first self-report of feeling recovered from symptoms related to COVID-19 or COVID-like-illness (for Phase IIb/III type evaluation).
- Viral clearance and potentially impact on biomarkers of illness severity (for Phase IIa type evaluation, assessed at baseline and on days 4, 7 and 14 or specified in ISA if samples will be taken on other days).

8.1.2 Secondary study parameters/endpoints include:

Key secondary outcome: early sustained recovery (recovery by day 14 sustained until day 28). Other secondary endpoints:

- Sustained recovery (participants' reported recovery that was maintained until 28 days)

- Time to first self-report of feeling recovered from symptoms of COVID-19 or COVIDlike-illness (for Phase IIa type evaluation)
- Viral clearance (for Phase IIb/III type evaluation, assessed at baseline and on days 4,
 7 and 14 or specified in ISA if samples will be taken on other days).
- Time to first self-report of return to usual daily activity.
- Presence, duration, and severity of individual respiratory symptoms (runny/congested nose, sore throat, cough, fever shortness of breath, fatigue/tiredness, sweats/chills, headache, muscle, joint and/or body aches, loss of taste/smell, diarrhoea, nausea/vomiting, other) as: absent, mild, moderate, severe.
- Participant reported overall wellbeing, reported by rating of how well participant feels (scale 0-10).
- Overall safety of the IP by reporting (serious) adverse drug reactions.
- The use of additional antiviral medication (yes/no, name of medication)
- The use of other prescribed and/or OTC medication for the respiratory infection (antibiotics, antiviral medication, ibuprofen, other pain/fever medication, inhaled medication, intranasal medication, other).
- Impact on usual daily activities (work/education, caring for (grand-) children, household activities, sports, social life), as: no, slight, moderate, severe, not applicable.
- Complications (hospitalisation, death; all-cause, non-elective hospitalisation).
- Health care utilisation for COVID-19 or COVID-like-illness (GP and hospital visits).

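### Section 9.2.3 gives two SAE exemptions of different scope, so the status of an elective admission for a new or worsened condition is unclear

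*Protocol*

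**What the plan says.** Protocol section 9.2.3 lists the criteria that make an untoward medical occurrence serious. One of them is that it "requires hospitalisation or prolongation of existing inpatients' hospitalisation". Directly after the list comes an exemption with no condition attached: "An elective hospital admission will not be considered as an SAE".

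The next paragraph sets the threshold for an admission: "Hospitalisations will be defined as at least one overnight stay". It then gives a second exemption: "Hospitalisation for a pre-existing condition, including elective procedures planned prior to study entry, which has not worsened, does not constitute an SAE".

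The word elective is not defined in the protocol. Section 9.2.3 also requires SAEs to reach the sponsor within 24 hours of awareness and to be reviewed by the medical monitor for relatedness and expectedness. Section 9.2.4 makes seriousness the first of three conditions for a SUSAR.

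**The concern.** The two exemptions differ in scope. The first depends only on whether the admission is elective. The second depends on whether the condition was already present and has stayed the same. If every elective admission were already exempt, the mention of pre-planned elective procedures in the second sentence, and its proviso that the condition has not worsened, would do no work for elective admissions. That wording suggests that some elective admissions were meant to count.

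Seriousness is the gate to expedited safety handling. If two sites apply different sentences to the same kind of admission, one files a 24-hour report and the other does not. Section 8.2.1 names seven countries, so differing local readings are foreseeable. The SAE table by arm in the annual safety report (section 9.4) would reflect the same inconsistency.

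**Working it through.** No figure in the protocol bears on this and no arithmetic applies. The check sets the two sentences side by side, case by case. Each case is taken to be an untoward medical occurrence with at least one overnight stay in the 28-day window, meeting no seriousness criterion other than hospitalisation.

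| Case | First sentence (elective) | Second sentence (unworsened pre-existing condition) | Result |
|---|---|---|---|
| 1. Elective, planned before entry, pre-existing condition unchanged | Exempt | Exempt | Agree |
| 2. Elective, arranged after entry, pre-existing condition unchanged | Exempt | Exempt, because planning before entry is an included example and not a condition | Agree |
| 3. Elective, pre-existing condition that has worsened | Exempt | Not exempt, so serious by the hospitalisation criterion | Diverge |
| 4. Elective, arranged after entry, new condition | Exempt | Not exempt, so serious by the hospitalisation criterion | Diverge |
| 5. Not elective, pre-existing condition unchanged | Silent | Exempt | No conflict |
| 6. Not elective, new or worsened condition | Silent | Not exempt | SAE |

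The divergence is confined to cases 3 and 4. What follows in those cases if a site applies the first sentence:

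- **24-hour report and medical-monitor review (section 9.2.3).** Both attach to SAEs, so neither is triggered.
- **SUSAR assessment (section 9.2.4).** Seriousness fails, so a related and unexpected event would not enter the 15-day route. The 7-day route is unaffected. It applies to fatal or life-threatening reactions, which are serious under their own criteria whatever the type of admission.
- **Ordinary AE recording (section 9.2.1).** This remains for up to 28 days, with a clinician's assessment of causality and severity. However, that section defines AEs as unrelated to the respiratory infection, so an admission for a consequence of the infection falls outside it.
- **Health care utilisation (sections 8.1.2 and 8.3.2).** Hospital visits for the illness are still collected, but no causality or expectedness review is attached to them.

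**The case against.** The strongest reply is that the second sentence nowhere says that it is the only exemption. Both sentences are exclusions and both can apply together, so the conflict arises by implication. This stands in part. A reader might infer that admissions of this kind are definitely lost from SAE reporting, and the text does not support that. They are lost if the first sentence governs and reportable if the second sets the limit. The supportable finding is unclear status.

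The reply also notes that the first sentence exempts the admission and not the underlying event, which may be serious on other grounds. That is right for fatal, life-threatening or disabling events. The residual route is less secure. It covers an event that "is any other important medical event that did not result in any of the outcomes listed above", and because hospitalisation is one of those outcomes, a site could read the route as closed. The sponsor's SOP or an intervention-specific appendix might also settle the matter. Neither is shown here, and the master protocol's own wording would still need to agree with itself.

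Two further inferences are tempting and should not be drawn:

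- **Complications endpoint.** Section 8.1.2 defines it as "Complications (hospitalisation, death; all-cause, non-elective hospitalisation", and section 2.2 says the same. That is a separate and consistent definition. It does not follow from section 9.2.3, would not change if that section were corrected, and is not part of this finding.
- **Mix of elective admissions.** Section 4.3 excludes patients with "Any planned major surgery in the next 28 days". A reader might conclude that elective admissions in follow-up are mostly newly arranged. The criterion covers major surgery only, so patients with other planned admissions remain eligible, and no figure supports a statement about proportions.

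**Conclusion.** The inconsistency is real, minor and cheap to remove. It affects elective overnight admissions within 28 days for a new or worsened condition. It has consequences only where the event meets no other seriousness criterion and the site follows the unqualified sentence. In that situation the 24-hour report, the medical monitor's review and any 15-day SUSAR assessment are missed. No 7-day SUSAR report can be lost this way.

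Few such events are expected in 28 days. That is an assumption: the protocol gives no admission or SAE rate, and section 4.4 leaves sample size to the intervention-specific appendices. No share of the SAE total can therefore be stated. The conclusion also assumes that the second sentence was meant to limit which elective admissions are exempt. That is the reading that gives its qualifiers a purpose, but the text does not state it outright.

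**What to change.** Reconcile the two sentences in section 9.2.3. Either delete the unqualified one, or limit it to admissions for a pre-existing condition that has not worsened. Deletion is simpler, since the limited version would add little to the second sentence. The result should be that an untoward medical occurrence leading to an overnight admission for a new or worsened condition is an SAE, whether or not the admission is called elective.

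The change should stop there. Planning before entry should stay an included example, because making it a requirement would turn case 2 into an SAE although the second sentence exempts it. Nor should every other overnight admission become an SAE without an untoward medical occurrence behind it.

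The cost is one sentence deleted or qualified, and possibly a few more SAE reports. Design, sample size and endpoints are unaffected.

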9.2.4 Suspected unexpected serious adverse reactions (SUSARs)

Unexpected adverse reactions are SUSARs if the following three conditions are met:

- 1. The event must be serious (see chapter 9.2.2)
- 2. There must be a certain degree of probability that the event is a harmful and an undesirable reaction to the IP under investigation, regardless of the administered dose
- 3. The event must be unexpected, that is to say, the nature and severity of the adverse reaction are not in agreement with the product information as recorded in:
 - SmPC for an authorised medicinal product
 - IB for an unauthorised medicinal product

All SUSARs will be reported by the Sponsor or delegate to the relevant CAs and/or IECs as per national regulations.

The period for the reporting of SUSARs by the Sponsor, taking into account the seriousness of the reaction, will be as follows:

- In the case of fatal or life-threatening SUSARs, as soon as possible and in any event not later than **7 days** after the Sponsor became aware of the reaction
- In the case of non-fatal or non-life-threatening SUSARs, not later than **15 days** after the Sponsor became aware of the reaction
- In the case of a SUSARs which was initially considered to be non-fatal or nonlife-threatening but which turns out to be fatal or life-threatening, as soon as possible and in any event not later than **7 days** after the Sponsor became aware of the reaction being fatal or lifethreatening

Where necessary to ensure timely reporting, the Sponsor may submit an initial incomplete report followed up by a complete report.

9.3 Unblinding procedures for safety reporting

The Site Investigator will only unblind the treatment allocation of a participant during the trial if unblinding is relevant to the safety of the participant and if knowledge of the treatment allocation could influence the immediate medical management of a participant. Emergency unblinding will be performed by the Site Investigator by either 1) opening the emergency unblinding envelope for that participant stored at the site; or 2) digitally using the randomisation tool; or 3) using a central phone number. Sites will be trained on which method for emergency unblinding to follow.

When reporting a SUSAR to the CAs as per national regulations, the Sponsor will only unblind the treatment allocation of the affected participant to whom the SUSAR relates.

Unblinded information will be accessible only to persons who need to be involved in the safety reporting to the CAs, to the DSMB, or to persons performing ongoing safety evaluations during the trial.

9.4 Annual safety report

In addition to SUSAR reporting, the Sponsor will submit a safety report to the accredited IEC and CAs of the participating countries (for the Member States concerned through CTIS), once a year.

This safety report consists of:

- a list of all suspected (unexpected or expected) serious adverse reactions, along with an aggregated summary table of all reported SAEs, ordered by organ system, per arm.

- a report concerning the safety of the participants, consisting of a complete safety analysis and an evaluation of the balance between the efficacy and the harmfulness of the IP under investigation.

9.5 Follow-up of SAEs

All SAEs will be followed until they have abated, or until a stable situation has been reached. Depending on the event, follow-up may require additional tests or medical procedures as indicated, and/or referral to the GP or a medical specialist.

All SAEs that have not resolved by the end of the study, those that are identified retrospectively, or that have not resolved upon trial discontinuation of the participant, must be followed until any of the following occurs:

- The event resolves
- The event stabilises
- The event returns to "baseline", if a "baseline" value/status is available
- The event can be attributed to agents other than the study intervention, or to factors unrelated to study conduct
- It becomes unlikely that any additional information can be obtained (participant or GP refusal to provide additional information, lost to follow-up after demonstration of due diligence with follow-up efforts).

9.6 Urgent safety measures and other relevant safety reporting

Where an unexpected event is likely to seriously affect the benefit-risk balance, the Sponsor and the Site Investigator(s) will take appropriate urgent safety measures to protect the participants. In addition, the Sponsor will notify the IECs and CAs of the participating countries of the event and the measures taken (for Member States concerned via CTIS). That notification will be made without undue delay but no later than **7 days** from the date the measures have been taken.

In case of data security breaches, the breach will be reported to the appropriate authority (e.g. Authoriteit Persoonsgegevens) as soon as possible, but at least within 72 hours after discovering the breach. If necessary, those affected by the breach will be informed. It will be agreed upon with participating NCTs and sites in the MSA/CTA that NCTs or sites will report data breaches concerning participant data to the Sponsor and inform applicable regulatory authorities.

9.7 Data Safety Monitoring Board

Given the adaptive nature of ECRAID-Prime, a DSMB will be set up that will review new ISAs and safety data. The DSMB is an independent committee; the chair will be selected based on clinical trial methodology, and experience with adaptive clinical trial design. Additional medical,

statistical, and other experts will be selected to ensure all necessary expertise. Members have no conflict of interest with the Sponsor of the study and IPs tested in the study.

The charter document describes the roles and responsibilities of the DSMB, including the timing of meetings, methods of providing information to and from the DSMB, frequency and format of meetings, statistical issues, and relationships with other committees. The DSMB will be unblinded to ensure the highest quality oversight of the trial, in accordance with current recommendations of regulatory authorities.

Possible recommendations of the DSMB could include:

- No action needed, trial continues as planned
- Early stopping due to, for example, clear benefit, futility, harm of an IP, or external evidence
- Stopping recruitment within a specific subgroup
- Extending recruitment (based on actual control arm outcomes being different to predicted rather than on emerging differences) or extending follow-up
- Stopping a single arm of a multi-arm trial
- Sanctioning and/or proposing protocol changes

The advice(s) of the DSMB will only be sent to the Sponsor of the study. Should the Sponsor decide not to fully implement the advice of the DSMB, the Sponsor will send the advice to the reviewing IECs, including a note to substantiate why (part of) the advice of the DSMB will not be followed.

10. STATISTICAL ANALYSIS

Full details of the statistical analysis will be described in the Master Statistical Analysis Plan (M-SAP). An appendix to the M-SAP titled "Simulation Report" provides simulation results that justify the sample size and design of the study. In addition, the M-SAP will be accompanied by arm-specific appendices to describe any planned deviations from the M-SAP. A broad overview of the design and primary analysis is provided below.

ECRAID-Prime is an adaptive platform trial with early stopping rules for futility or superiority. Comparisons will be based on concurrent and eligible controls only, where control is either a (matched) placebo or comparator, or, if deemed necessary, Usual Care. If there are 2 matched placebos with concurrent randomisation, the primary analysis will pool controls unless it is decided otherwise and specified in the ISA. We may carry out sensitivity analyses with matched controls only included. Early stopping rules will be based on posterior probabilities with thresholds defined using simulations to ensure good trial performance with respect to power and type 1 error.

Each treatment will be analysed separately.

Baseline characteristics will be summarised by IP arm. Continuous variables will be presented as means and standard deviations (or medians and inter-quartile ranges for skewed data). Categorical and binary data will be presented as frequencies and percentages. AEs and SAEs will be summarised by treatment arm.

